#### 8.3 Data Analysis Plans

Primary analyses will include 1) estimating the sensitivity of CEUS qualitative interpretations using the gold standard of findings on 1-yr follow-up non-contrasted US compared to baseline non-contrasted US and 2) estimating the sensitivity of various quantitative metrics derived from CEUS images using the gold standard of findings on 1-yr follow-up non-contrasted US compared to baseline non-contrasted US compared to baseline non-contrasted US images using the gold standard of findings on 1-yr follow-up non-contrasted US compared to baseline non-contrasted US.

Descriptive summary statistics such as mean, median and standard deviation of tumor measurement will be provided to quantify and characterize kidney lesions.

#### CONFIDENTIAL UNIVERSITY OF NORTH CAROLINA

Similarly, other patient clinical and demographic characteristics will be summarized, using frequencies in the case of categorical variables.

For Aim 1, sensitivity and specificity and their 95% confidence intervals will be computed for CEUS qualitative interpretations compared to change in baseline noncontrasted US. Based on the gold standard diagnosis of lesion progression at one vear follow-up, a 95% confidence interval for the Mantel-Haenszel odds ratio will be constructed to quantify the odds that a subject with a diagnosis of a malignant lesion by non-contrasted US will be diagnosed with a malignant lesion by CEUS relative to the odds for a subject without a malignant lesion diagnosis by non-contrasted US. A similar odds ratio and 95% confidence interval will be constructed for subjects with a gold standard diagnosis of stable or lesion regression. Sensitivities, specificities are based on diagnoses made using CEUS-based risk classification (class I, II, and IIF considered negative, class III and IV as positive, using modified Bosniak criteria). Estimation of sensitivity and specificity will be carried out for each reader, two per site. Agreement between readers will be based on kappa statistics for the dichotomous diagnosis and using weighted kappas based on the ordinal Bosniak scale. Inter-institutional agreement will be assessed using kappa statistics by sending all decoded images from UNC to Vanderbilt and vice versa.

For Aim 2, the prediction performance of quantitative CEUS metrics (including but not limited to wash-in rate, time-to-peak intensity, and wash-out rate) will be assessed with ROC analysis based on area-under-the-curve (AUC) for each metric. Meaningful cutoff points will be determined for the metrics such that sensitivity is at least 80%, the lower end of sensitivity of contrast-enhanced CT in a general population) without decreasing specificity to below 60%. Confidence intervals for sensitivities and specificities based upon these cutoffs will be calculated to determine if one is better than the others. Additionally, multiple logistic regression analysis will be performed with the gold standard diagnosis of lesion progression as outcome to determine whether multiple metrics improves AUC. The ROC in this case is determined by applying different cutoffs to the model-predicted probability of lesion progression where the multiple metrics serve as the independent variables in the model. We will also determine if the predictive model can be improved by inclusion of patient demographic and clinical variables.

As part of a secondary sensitivity analysis, the sensitivity of CEUS, both qualitative interpretations and quantitative metrics, will be compared to the sensitivity when other standards are incorporated when available, including pathology and additional imaging with contrasted or non-contrasted CT or MR.

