#### 2.2 Secondary Objectives

To estimate the sensitivity and specificity of quantitative metrics generated from CEUS in diagnosing kidney malignancy in patients with CKD and a suspicious or indeterminate lesion on non-contrasted imaging compared to the truth standard described in 1.4 and 4.2.6. We will also compare sensitivity and specificity of quantitative metrics to the sensitivity and specificity of the qualitative interpretations.

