#### CONFIDENTIAL UNIVERSITY OF NORTH CAROLINA

#### 4.0 STUDY PLAN

#### 4.1 Schema

Patients who meet study inclusion and exclusion criteria (see Sections 3.1 and 3.2) and provide informed consent will be subjected to a baseline conventional, non-contrasted ultrasound on Day 1. Following the non-contrasted ultrasound, CEUS will be performed on the identified lesion of interest. One year after initial study, a follow-up non-contrasted ultrasound will be obtained. The results of any other additional studies obtained clinically, including histology, contrasted or non-contrasted CT/MR, will be collected. Once all CEUS studies are completed, blinded radiologists will grade each lesion based on Bosniak criteria. Once all follow-up non-contrasted ultrasounds are obtained, radiologists will grade each lesion as stable, progressed, or regressed.

Please see the Time and Events Table in Appendix 2 for a full listing of evaluations and assessments throughout the course of the study.

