#### 4.2.5 Assessment of Imaged Lesions

Two blinded radiologists at each institution (UNC and VU) will interpret the US images independently. Each interpreter will be asked to assess multiple lesion characteristics including echogenicity, size, septations, vascularity, and patterns of

enhancement which will be used to classify the lesion into a Bosniak category. A diagnostic conclusion (e.g. benign, malignant, or indeterminate lesion) will be derived based on the Bosniak category. Bosniak categories I, II and IIF will be classified as benign, and categories III and IV as malignant. The Bosniak classification system can be found in Appendix I.

Results of the perflutren-enhanced scans will not be used to dictate treatment and will not be shared with patients.

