#### 8.2 Sample Size and Accrual

This study will recruit to a target goal of 75 patients total between the primary site (UNC) and Affiliate (VU). We expect to complete the enrollment in about 6 months. Based on available literature regarding incidence of malignancy in indeterminate (Bosniak IIF and III) lesions and accuracy of CEUS for cystic kidney lesion characterization in a general, non-CKD population and our experience from a pilot study including 27 patients with kidney disease and an indeterminate lesion, we approximate a true positive rate of 10%, false positive rate of 8%, true negative rate of 80% and false negative rate of 2%. Given the sample size of 75 (allowing for 10 to be lost to follow-up/death) and these approximated rates, we project an achievable sensitivity of 83%, specificity of 91%, PPV of 56% and NPV of 98%. The 95% confidence interval for this sensitivity estimate is 74.5-91.5% with a width of 17%.

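### Do the four-reader CEUS analyses in 8.3 and 2.2 need a named reader summary, Mantel-Haenszel strata and a lesion rule?

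*Combined protocol and SAP*

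**What the plan says.** Section 4.2.5 sets up the readings: "Two blinded radiologists at each institution (UNC and VU) will interpret the US images independently". For Aim 1, section 8.3 says that "Estimation of sensitivity and specificity will be carried out for each reader, two per site". Agreement is measured by kappa for the two-way diagnosis and weighted kappa for the Bosniak grade. Images are also exchanged between the sites for an inter-institutional kappa, so a lesion may have up to four readings.

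The same paragraph of 8.3 says that "a 95% confidence interval for the Mantel-Haenszel odds ratio will be constructed to quantify the odds that a subject" with a malignant result on non-contrasted US is also called malignant by CEUS, relative to a subject without one. A similar odds ratio follows for subjects whose lesion was stable or regressed. So two odds ratios are planned. Both are worded per subject, and neither has a named stratification factor.

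Two comparisons use the qualitative result without saying whose reading it is. Section 2.2 states: "We will also compare sensitivity and specificity of quantitative metrics to the sensitivity and specificity of the qualitative interpretations". The last paragraph of 8.3 states that "the sensitivity of CEUS, both qualitative interpretations and quantitative metrics, will be compared to the sensitivity when other standards are incorporated when available".

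On the unit, 8.2 counts patients. In 4.1, "Following the non-contrasted ultrasound, CEUS will be performed on the identified lesion of interest", and later, "Once all CEUS studies are completed, blinded radiologists will grade each lesion based on Bosniak criteria". Section 4.2.4 lets a patient with several lesions have a second contrast study, and 9.3 codes each lesion by patient number plus a letter.

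**The concern.** Four readers produce four sets of diagnoses, and the only thing linking them is kappa, which measures agreement and does not yield a combined result. Yet an odds ratio for a subject diagnosed by CEUS, and a comparison of metrics with the qualitative reading, both seem to need one result per subject. Mantel-Haenszel is a stratified estimator, so leaving the strata unnamed adds to the doubt.

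Two things could go wrong. A merging rule chosen after the readings are seen could move the reported sensitivity. Or an analyst could use the readers as strata, count each subject up to four times and report an interval that is too narrow. Patients with two imaged lesions raise the same question of dependence.

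**Working it through.** **Inputs.** From 8.2: true positives 10%, false positives 8%, true negatives 80%, false negatives 2%; 75 patients with 10 allowed for loss, so 65. From 4.2.5 and 8.3: two readers at each of two sites. Not in the documents: r, the correlation between two readers' binary calls given the truth, defined by P(both positive) = p² + r·p(1−p). It is an assumption, taken over 0.4 to 0.9.

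**1. The plan's own figures.** Sensitivity 10/12 = 83.3%, specificity 80/88 = 90.9%, PPV 10/18 = 55.6%, NPV 80/82 = 97.6%. The interval is 0.83 ± 1.96·√(0.83×0.17/75) = 0.83 ± 0.085, that is 74.5 to 91.5%. All agree with 8.2. (Whether 75 is the right denominator for that interval is a separate matter.)

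**2. The per-reader estimates.** Each reader's expected sensitivity is 83.3% and specificity 90.9% for any r. No merging rule enters.

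**3. What a merging rule would do.** For two readers, the sensitivity gap between the either-reader and both-readers rules is 2p(1−p)(1−r), with p(1−p) = (5/6)(1/6) = 0.1389. The specificity gap uses (10/11)(1/11) = 0.0826.

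| r | Sensitivity, either / both | Gap (points) | Specificity gap (points) |
|---|---|---|---|
| 0.4 | 91.7% / 75.0% | 16.7 | 9.9 |
| 0.6 | 88.9% / 77.8% | 11.1 | 6.6 |
| 0.9 | 84.7% / 81.9% | 2.8 | 1.7 |

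These gaps are systematic, but they arise only if a rule is applied, and 8.3 applies none.

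**4. The odds ratio.** On the ordinary two-by-two reading it is [sensitivity/(1−sensitivity)] × [specificity/(1−specificity)] = 5 × 10 = 50, a function of the two quantities already reported for each reader. With one reading per subject and N = 75 the cells are 7.5, 6, 1.5 and 60. The SE of the log odds ratio is √(1/7.5 + 1/6 + 1/1.5 + 1/60) = 0.992, and the 95% CI is 7.2 to 349. Four readings treated as independent would halve the SE and give 18.9 to 132. In simulation with 65 subjects and readers as strata, the standard interval covers 88%, 83% and 78% at r = 0.4, 0.6 and 0.9, counting only the trials where it is defined (93.5%, 89.6% and 78.9%). That would be an error, but no section makes readers the strata. With no strata, Mantel-Haenszel reduces to the crude odds ratio; site is the other natural choice.

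**5. Empty cells.** One reader's table has no false negatives with probability (1 − 0.12/6)^65 = 0.98^65 = 26.9%. Now take a consensus in which a third read settles disagreements, and let each reader share a common draw with probability √r. At r = 0.6, √r = 0.775. The chance that at most one of three readers uses the shared draw is 0.225³ + 3×0.775×0.225² = 0.13, and the majority is then right with probability (5/6)³ + 3(5/6)²(1/6) = 0.926. Consensus sensitivity is 0.13×0.926 + 0.87×0.833 = 0.845, and no false negatives occur with probability (1 − 0.12×0.155)^65 = 30%. At r = 0.4 and 0.9 the figures are 34% and 27%. The cause is the expected number of positives, 0.12 × 65 = 7.8, and a reader summary does not change it.

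**6. The comparison in 2.2.** If a metric has sensitivity 80 to 90% (assumed), it beats one reader and loses to another in 8 to 9% of simulated trials at r = 0.6, and in 1 to 16% over the range of r. A per-reader comparison would show this openly.

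**7. The unit.** The two sentences in 4.1 are compatible: one describes a single examination, the other the set of lesions graded in the study. What remains is the patient with two imaged lesions. The documents give no count of such patients, so the effect cannot be sized. The lesion codes in 9.3 carry the patient number, so one lesion per patient or a patient-clustered interval is available at analysis.

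**The case for a change.** The strongest case for a change is that no section states a rule, that a rule chosen late could move sensitivity by 11 points at r = 0.6, and that a few sentences would prevent it. Images are already exchanged, and a consensus would need a third read in only about 65 × 0.4 × (0.12×2×0.1389 + 0.88×2×0.0826) = 4.6 subjects (1.2 to 7.0 over the range of r).

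Part of this stands. The reader, the strata and the handling of two lesions are unwritten, and repeated readings of one subject must not be treated as independent.

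The rest is weaker than it looks. The headline estimates are fixed as per reader, so there is no merged sensitivity to select. The choice of summary is a trade-off: a consensus describes a panel rather than a radiologist, while an average gives no diagnosis for an individual subject. The average may also need about one more read per lesion if only one reader at each site reads the exchanged images. Nor would naming a reader tidy the odds-ratio sentences. Read literally, they place each odds ratio within a truth-standard group that is itself defined by non-contrasted US, so the analyst has to take the ordinary two-by-two reading whichever readings are used.

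**Conclusion.** No change is needed. The primary sensitivity and specificity are complete as planned: one estimate per reader, with agreement reported beside it. The odds ratios and comparisons can be done reader by reader, or with a crude or site-stratified odds ratio, without departing from the text. The 3 to 17 point spread between merging rules and the 78 to 88% coverage belong to analyses that the plan does not state, and both rest on an assumed r of 0.4 to 0.9. The empty-cell problem, 27% for one reader and 27 to 34% under consensus, comes from about 8 expected positives. Section 8.1 describes a pilot meant to estimate sensitivity, with no hypothesis test that hangs on a single merged reading. The conclusion assumes that the analyst does not pool readings of one subject as independent and accounts for a second lesion in the same patient, which is ordinary practice.

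### Aim 2 tunes cutoffs and judges multi-metric AUC on the same lesions with no validation step, so tuned sensitivity and fitted-model AUC are optimistic

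*Combined protocol and SAP*

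**What the plan says.** Aim 2 in section 8.3 assesses each quantitative metric by its AUC. The list of metrics is open: "including but not limited to wash-in rate, time-to-peak intensity, and wash-out rate". Cutoffs come next: "Meaningful cutoff points will be determined for the metrics such that sensitivity is at least 80" percent, "without decreasing specificity to below 60" percent. The cutoffs then carry the inference: "Confidence intervals for sensitivities and specificities based upon these cutoffs will be calculated to determine if one is better than the others".

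For combinations of metrics, "multiple logistic regression analysis will be performed with the gold standard diagnosis of lesion progression as outcome to determine whether multiple metrics improves AUC"; its ROC curve is traced by moving a threshold along that model's predicted probability. Then: "We will also determine if the predictive model can be improved by inclusion of patient demographic and clinical variables".

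Section 2.2 adds a further use: "We will also compare sensitivity and specificity of quantitative metrics to the sensitivity and specificity of the qualitative interpretations". The qualitative read has its threshold fixed beforehand ("class I, II, and IIF considered negative, class III and IV as positive, using modified Bosniak criteria").

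No section gives a hold-out sample, cross-validation, bootstrap correction, shrinkage, a cutoff fixed in advance, a limit on predictors, or a rule for when AUC counts as improved. The second site (4.2.2) serves enrolment and imaging, and the exchange of images between sites (8.3, Aim 1) serves reader agreement. Neither is assigned to validation. Section 8.3 also does not say what is reported when no cutoff meets both limits.

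**The concern.** A cutoff chosen because it reaches a target sensitivity on a set of lesions cannot then be tested for sensitivity on that set: the result is built in. A regression model fitted to few events ranks those events better than it will rank new ones. Both effects grow as events become fewer, and few are expected here.

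Tuned metrics would be reported at 80% sensitivity or more, and combined models with a higher AUC than they would have in new patients. An ordinary confidence interval at the tuned cutoff shows imprecision but does not remove this bias. A pilot's figures are likely to guide which metric or model is carried forward, and nothing in the plan warns that these figures are fitted. In the comparison of section 2.2, a data-tuned sensitivity is set beside one from a threshold fixed in advance.

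**Working it through.** **The plan's own figures.** Section 8.2 assumes 10% true positives, 8% false positives, 80% true negatives and 2% false negatives. Sensitivity = 10/(10+2) = 83%, specificity = 80/(80+8) = 91%, PPV = 10/18 = 56%, NPV = 80/82 = 98%; all four reproduce. The stated interval is 0.83 ± 1.96 × √(0.83 × 0.17/75) = 74.5% to 91.5%, which uses all 75 patients as the denominator. That is a separate matter. The plan gives no precision figure for Aim 2.

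**Expected events.** Evaluable patients: 75 − 10 = 65. Positives: 10% + 2% = 12%. Events: 0.12 × 65 = 7.8, with a 95% binomial range of 3 to 13. The 12% is a malignancy rate and stands in here for progression on one-year ultrasound, which is the event that section 4.2.6 defines.

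**Tuned sensitivity.** If the cutoff sits at the r-th highest value among E progressions, observed sensitivity is r/E and mean sensitivity in new lesions is r/(E+1). Taking the smallest r with r/E at least 0.80:

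| Events | r | Shown | Mean true |
|---|---|---|---|
| 5 | 4 | 80% | 4/6 = 67% |
| 8 | 7 | 87.5% | 7/9 = 78% |
| 13 | 11 | 85% | 11/14 = 79% |

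With 8 events, the only other cutoff that qualifies is 8/8, which shows 100% against 8/9 = 89%. The exact 95% interval for 7/8 is 47.3% to 99.7%.

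**Effect of the specificity floor.** Simulation with 8 progressions, 57 non-progressions, normally distributed metrics and the cutoff at 7/8:

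| True AUC | Share meeting the 60% floor | Mean true sensitivity of those that meet it |
|---|---|---|
| 0.75 | 38% | 65% |
| 0.80 | 57% | 69% |
| 0.85 | 75% | 73% |

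Over all metrics the mean stays at 78%. At AUC 0.80, for example, the metrics that miss the floor must average (0.778 − 0.565 × 0.694)/0.435 = 89%. Specificity is nearly unbiased: at AUC 0.80 it is 62.0% observed and 62.0% true over all metrics, and 75.0% against 73.5% among those that meet the floor.

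**Fitted-model AUC.** Logistic model, 8 events of 65. Apparent AUC is measured on the fitting data; true AUC is that of the same fitted score in new patients.

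| Metrics in the model | Apparent | True | Gap |
|---|---|---|---|
| One of AUC 0.75 plus two of noise | 0.789 | 0.710 | 0.08 |
| One of AUC 0.75 plus four of noise | 0.819 | 0.686 | 0.13 |
| Three of AUC 0.75, independent | 0.894 | 0.856 | 0.04 |
| Three of AUC 0.75, correlation 0.5 | 0.827 | 0.764 | 0.06 |
| Three of AUC 0.75, correlation 0.8 | 0.801 | 0.729 | 0.07 |

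The optimism is present in every row. In the third row the combined model is also truly better than a single metric.

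**The case against.** The strongest reply is that the consequences are bounded. Section 8.1 calls the study a pilot, section 2.2 makes the metrics a secondary objective, section 4.2.5 keeps scan results out of treatment decisions, and an interval as wide as 47.3% to 99.7% invites no confidence. All of this stands, and it limits the weight of the point. Section 8.3 does list the metrics' sensitivity among the primary analyses, but that sentence is visibly repetitive and sits awkwardly with section 2.2, so little should rest on it. None of this removes the bias or labels the figures as fitted.

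A reader might infer more than the documents support, in four ways.

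- *That tuned metrics truly reach only about 65% to 73%.* This holds only if metrics missing the 60% floor are set aside. The plan does not say so. Without that step the mean is 78% at 7/8 and 89% at 8/8. Placing the cutoff as high as the target allows is also an assumption.
- *That a false improvement in AUC is almost certain.* Any numerical rise occurs in about 84% of simulated trials with three metrics and 95% with five, but only when the added metrics are pure noise and any rise counts. By likelihood-ratio test the rate is about 6% to 8% with three metrics and 8% to 11% with five. What the plan lacks is a criterion, so no rate can be attributed to it.
- *That the comparison with the qualitative read favours the metrics overall.* Only its sensitivity half is tilted. Against a read at the plan's 83% and 91%, metrics that meet the floor look less specific in 96%, 92% and 85% of trials at AUC 0.75, 0.80 and 0.85. They look more sensitive and at least as specific in only 2%, 3% and 6%. These rates assume that metric and read are independent, although both come from the same images.
- *That every AUC in Aim 2 is inflated.* The AUC of one metric with a prespecified direction is not.

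**Conclusion.** The concern holds in this form: under Aim 2 as written, sensitivity at a tuned cutoff and AUC of a fitted multi-metric model would be reported from the data that produced them, without correction. With 8 events, 87.5% would be shown where the mean true value is 78%. Three-metric AUC would be about 0.04 to 0.08 too high, and more with more predictors. Per-metric AUC and specificity at the cutoff are essentially sound.

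The sizes rest on 65 evaluable patients with one lesion each, a 12% event rate borrowed from malignancy, normally distributed metrics, and assumed AUCs and correlations. The direction did not change in any case tried. This should be corrected in the plan, but it does not threaten the study's main estimate from the qualitative read.

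**What to change.** In section 8.3, Aim 2:

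1. Report bootstrap optimism-corrected or repeated cross-validated AUC for the multi-metric models and for those extended with demographic and clinical variables. Resample by patient, not by lesion, because sections 4.2.4 and 9.3 allow several lesions per patient. Repeat any selection of metrics within each resample. State in advance what counts as an improved AUC and apply that criterion to the corrected value; a likelihood-ratio test for the added terms may accompany it.
2. Label cutoff-based sensitivities and multi-metric results exploratory, and state that sensitivity at a tuned cutoff is set by the rule. Compare metrics with each other mainly on AUC. Any comparison with the qualitative read at a matched sensitivity should be paired and labelled as also tuned on the same data.
3. Report all metrics, including those for which no cutoff meets both 80% and 60%. If a corrected sensitivity is given, repeat both the cutoff choice and the floor in each resample and say that the correction is partial.

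The cost is some analysis code and a few sentences; no new data are needed. The figures become less favourable and stay imprecise. In simulation with 8 events and one useful metric plus noise, bootstrap correction moved the three-metric AUC from 0.79 to 0.72 (true 0.71) and the five-metric AUC from 0.82 to 0.71 (true 0.68). The corrected AUC still exceeded that of the single metric in 25% and 27% of trials. For tuned sensitivity among metrics that meet the floor, it moved 87.5% only to about 76%, against true values of 65%, 69% and 73% at AUC 0.75, 0.80 and 0.85. That is why labelling is the main remedy there.

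### Aim 2 picks the better quantitative metric from separate confidence intervals at cutoffs tuned to sensitivity in the same data, and 8.3 has no method for the comparison with the qualitative reads promised in 2.2

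*Combined protocol and SAP*

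**What the plan says.** Section 2.2 sets a secondary comparison: "We will also compare sensitivity and specificity of quantitative metrics to the sensitivity and specificity of the qualitative interpretations".

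Section 8.3 describes the second analysis as "estimating the sensitivity of various quantitative metrics derived from CEUS images", judged against the same one-year change on non-contrasted ultrasound as the reads. For Aim 2 it assesses each metric by AUC. The list of metrics is open ("including but not limited to wash-in rate, time-to-peak intensity, and wash-out rate"). It then sets a cutoff rule, "Meaningful cutoff points will be determined for the metrics such that sensitivity is at least 80" percent, "without decreasing specificity to below 60" percent, and follows it with the decision sentence: "Confidence intervals for sensitivities and specificities based upon these cutoffs will be calculated to determine if one is better than the others".

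A multiple logistic regression then asks whether combining metrics raises the AUC. Reads are dichotomised by a Bosniak rule fixed in advance (4.2.5, 8.3), and their accuracy is estimated for each reader, two per site. Kappa is planned only for agreement between readers and institutions. No paired test, interval for a difference, paired AUC comparison or validation of the cutoffs appears.

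**The concern.** There are three problems.

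1. Each metric's sensitivity is compared after its cutoff has been chosen, in the same data, to make that sensitivity high. What is then compared is largely the selection rule.
2. The metrics come from the same lesions, so the relevant quantity is a within-lesion difference. One interval per estimate is not an interval for that difference.
3. The comparison in 2.2 has no analysis in 8.3. If the tuned metrics are simply set beside the Bosniak reads, the metrics have had their sensitivity optimised on the data and the reads have not.

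At stake is whether the study can say which metric to carry forward, and whether quantification adds anything to the radiologist's read.

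**Working it through.** **1. The plan's own figures (8.2).** The assumed rates are true positive 10%, false positive 8%, true negative 80% and false negative 2%. Sensitivity = 10/(10+2) = 83% and specificity = 80/(80+8) = 91%, as stated. The stated interval reproduces as 0.83 ± 1.96 × √(0.83 × 0.17/75) = 74.5 to 91.5%. Its denominator is all 75 enrolled, not those who progress. The documents give no power or interval for either comparison discussed here.

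**2. Counts.** Evaluable: 75 − 10 = 65. Progressors: 0.12 × 65 = 7.8, about 8. Non-progressors: 65 − 8 = 57. With no losses, progressors are 0.12 × 75 = 9. One lesion per patient is assumed.

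**3. Which sensitivities can qualify.** With 8 progressors, 6/8 = 75% fails the 80% rule. Only two values remain:
- 7/8 = 87.5%, exact 95% CI 47.3 to 99.7%
- 8/8 = 100%, exact 95% CI 63.1 to 100%

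These intervals always overlap. With 9 progressors, 7/9 = 77.8% fails, leaving 8/9 (51.8 to 99.7%) and 9/9 (66.4 to 100%), with the same result.

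**4. Optimism.** Assume a continuous metric, cut at the most specific point that meets the rule. With 8 progressors the cutoff is the second-lowest progressor value, so apparent sensitivity is always 7/8 = 87.5%. A new progressor lies above that value with expected probability 1 − 2/9 = 77.8%. A simulation (20,000 runs, binormal metric, true AUC 0.5 to 0.9) agrees: apparent sensitivity 87.5% with SD 0 at every AUC, true sensitivity about 78%, and true sensitivity below 80% in about half of runs. With 9 progressors the figures are 88.9% apparent and 1 − 2/10 = 80% true.

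Specificity at the same cutoff was not biased for a single metric cut once. At AUC 0.8, apparent and true specificity were both 62.1%.

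**5. Specificity: separate intervals against a difference.** Inputs are 57 non-progressors, 91% (from the plan's rates) against 75% (assumed), and latent normal correlations of 0, 0.5 and 0.8 (assumed). With b and c the two discordant counts, the rules are:
- Separate Wald CIs do not overlap: |p1 − p2| > 1.96 (SE1 + SE2)
- Unpaired Wald CI for the difference excludes zero: |p1 − p2| > 1.96 √(SE1² + SE2²)
- Exact McNemar: 2 × P(Bin(b + c, 0.5) ≤ min(b, c)) ≤ 0.05

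Power is the sum of the multinomial probabilities of all paired tables that meet the rule. The exact-CI row is simulated.

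| Rule | corr. 0 | 0.5 | 0.8 |
|---|---|---|---|
| Separate exact CIs do not overlap | 22% | 19% | 16% |
| Separate Wald CIs do not overlap | 37% | 35% | 32% |
| Unpaired CI for the difference | 66% | 68% | 71% |
| Exact McNemar | 54% | 66% | 82% |
| Asymptotic McNemar | 63% | 75% | 89% |

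At zero correlation the whole gain comes from testing the difference. Pairing adds to it as the correlation rises.

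**6. Sensitivity, paired.** Exact McNemar gives 2 × 0.5⁵ = 0.0625 for 5 discordant lesions all in one direction and 2 × 0.5⁶ = 0.031 for 6. At least 6 of 8 progressors would have to disagree, all the same way. Simulated power for 83% against 50% is 2 to 4%.

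**The case against.** Section 8.1 calls this a pilot designed to estimate sensitivity, the comparison is secondary, and no power is claimed for it. That limits the weight of the point. It does not excuse the method, because 2.2 and 8.3 both commit to comparing.

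Four stronger readings are tempting, and the documents do not support them.

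- A reader might infer that 8.3 uses separate intervals to decide between metrics and qualitative reads. In context the decision sentence refers to the metric cutoffs, so it compares metrics with one another. For metrics against reads the defect is an omission.
- A reader might infer that all of Aim 2 is circular. It is not: AUC needs no cutoff, the 60% specificity floor can exclude a poor metric (at true AUC 0.5, 1.2% of simulated runs met it), and specificity at similar sensitivity is still informative. Circularity is complete only for sensitivity between metrics. Against the reads it is a one-sided bias.
- A reader might infer a stated overlap rule. Section 8.3 says only that intervals will be calculated. Overlap is the natural use of separate intervals, but the power figures for it depend on that reading.
- A reader might infer that ignoring the pairing throws away most of the power. The table does not show that: at zero correlation, Wald overlap keeps 37% against 54% for exact McNemar, and an unpaired interval for the difference already recovers much of the loss.

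It is also fair to say that pairing does not rescue the sensitivity comparison. Step 6 confirms this, so the remedy should not claim otherwise.

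**Conclusion.** The concern holds in a limited form. The decision sentence in Aim 2 cannot identify a better metric on sensitivity: with about 8 progressors, qualifying metrics can differ only as 7/8 against 8/8. Tuned sensitivity overstates true sensitivity by about 10 points (87.5% against 77.8%) under the cutoff convention in step 4, which would favour the metrics over the fixed Bosniak rule. For specificity, judging by overlap of Wald intervals gives about 32 to 37% power for 91% against 75%, compared with about 54 to 82% by exact McNemar. The comparison promised in 2.2 has no stated analysis and no named comparator read.

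The counts rest on the plan's own rates. The 75% specificity, the correlations, one lesion per patient and the overlap criterion are assumptions. The point should be corrected before analysis. It does not affect the primary estimate of qualitative accuracy.

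**What to change.** Replace the decision sentence in 8.3 with these specifications:

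- Compare metrics by paired differences with 95% CIs: AUC by DeLong or paired bootstrap, and specificity at matched sensitivity by McNemar or paired bootstrap.
- Repeat cutoff selection inside every bootstrap or cross-validation sample, and report the optimism-corrected sensitivity and specificity.
- Resample by patient. Sections 4.2.4 and 9.3 allow several lesions per patient, and lesion-level McNemar or DeLong would ignore that clustering.
- Use the same paired method for metric against qualitative read. Name the comparator in advance, either one specified read or the reader average.
- Report sensitivity differences descriptively with intervals and no test, since about 8 progressors cannot support one.

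The cost is SAP wording and some extra analysis code, with no additional patients or data. The one drawback for the investigators is that corrected sensitivities will look less favourable than the tuned ones.
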